There are 2 main approaches to orbital fracture management. The traditional approach involves the use of a standard stock orbital plate, which is adapted intraoperatively to the fractured orbit. The advantages of this approach are that the plates are readily available, cheap, and require minimum peri-operative planning. The major drawback of the traditional approach is the inaccurate nature of reconstruction. It is often challenging to restore the orbital volume using this approach, and failure to restore volume results in post-operative enophthalmos.⁽¹²⁾ The second approach uses CAD/CAM technology (computer-aided design/computer-aided manufacturing technology). In this approach, a virtual plan is developed based on the patient's

CT scans. A 3D stereolithographic model is then fabricated, and a patient-specific titanium orbital implant is manufactured. These implants are manufactured using a selective laser melting process (KLS Martin, Tuttlingen, Germany). ^(11, 12) The CAD/CAM technology is currently considered to be the most accurate method of orbital reconstruction. ^(11, 21) The advantage of this approach is that it is patient-specific and therefore very accurate. However, the CAD/CAM technology is exceedingly expensive (depending on the vendor from \$6,995 to \$10,956.40 per case) with long production times (7–14 days). Reconstruction of the orbital fracture is time-sensitive to prevent unfavorable long-term sequelae; thus, CAD/CAM technology in orbital fractures has limitations due to production time. The second limitation of this approach is the cost. Fortunately, this technology is available today at a **low cost and high resolution due to office-based three-dimensional printing (3DP)**.

In this study, we propose a third approach to manage orbital fractures. This approach involves a **patient-specific pre-adjusted (pre-bend) orbital plate** utilizing an office-based 3DP. The approach is patient-specific because the orbital plate is preoperatively adjusted (pre-bend) to the patient's anatomic model; **this decreases the OR time and increases the accuracy of reconstruction**. The cost of 3D printing the patient's fractured orbital floor in the office is **significantly less than** the cost of utilizing the CAD/CAM technology for one patient. **The 3D printed model will cost at most \$1,374.5 (\$1.50 printed model + \$1,364 for the stock titanium implant) vs. \$2,800 for VSP utilizing a stereolithographic model with a patient-specific implant.**

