With such a 3D printer, true-to-life anatomic models can be made on-site within hours, and a patient with an orbital fracture can undergo reconstruction with a customized and personalized implant. An important difference compared with the virtual surgical planning (VSP) stereolithographic model is that the titanium implant is not milled on the model in 3DP. We use the over-the-counter titanium plates that are manually adjusted according to the printed model. We then send the plates to sterilization for preparation. Notably, this technology and method are yet to be applied to traumatic orbital floor fractures. Thus, to the best of our knowledge, this study is the first of its kind.

The purpose of this study is to compare (pre-bend) patient-specific orbital implants utilizing an office-based 3-D printer with standard non-adapted orbital implants (traditional approach). We will 1) preoperatively generate a patient-specific model to pre-adapt the titanium mesh to be used in unilateral orbital fractures; 2) accurately restore the orbital volume to the pre-injured measures; 3) prevent post-operative complications in terms of enophthalmos and diplopia; and 4) decrease the operative time, therefore decreasing the overall cost and increasing the value. Our patients greatly benefit from a fast and cost-effective method of reconstructing orbital floors due to the high volume and urban patient population of GMH.

METHODOLOGY

Study Settings and Patients

This is a prospective randomized clinical study with longitudinal follow-up. The study duration is 2 years. It will be conducted at GMH within the Grady Health System. The study targets urban adults suffering blunt facial trauma who are diagnosed with unilateral orbital fracture. Patients will be randomized into one of the following groups:

- Group A: patients who have orbital reconstruction utilizing **pre-adjusted patient-specific orbital implants with OB3DP (Treatment Group)**.

- Group B: patients who have orbital reconstruction utilizing **non-patient-specific** orbital implants (traditional approach) (**Control Group**).

The primary predictor variable is the treatment group (pre-adjusted patient-specific orbital implants utilizing OB3DP vs. non-patient-specific orbital implants).

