We expect a **sample size of 60** surgical cases, evenly split between the new treatment and control groups, to have a study powered to **detect at least a 1 cm³ difference in orbital volume** between the groups. The sample size calculation was based on using a two-sample Student's t-test to compare the difference in contralateral orbital volume between the treatment and control groups. We used a **power of 90%**, alpha level of .05, and 1.17 cm³ standard deviation of orbital volume. The 'normal' orbital volume and standard deviation were estimated from the results of Forbes et al. (1984). Sample size calculations were performed with the 'power.t.test' function in R statistical software based on Cohen (1988).⁽²⁵⁾ Taking attrition into account, if 25% of our expected patient enrollment numbers are not met for any reason, **our study would still retain a power of 80%**. Additionally, in the event of attrition from loss-to-follow-up alone, our primary outcomes variable and the bulk of the secondary outcomes variables, including the reduction of orbital volume to less than 2 cm³, operative time, traumatic pupillary mydriasis, orbital compartment syndrome, extra-ocular motility, and plate contour, will be successfully obtained on immediate post-operative hour. **Attrition at these stages will have no effect on the above variables.**

Randomization & Statistical Analysis

Cases will be randomized to the treatment or control arms using a pre-generated block randomization scheme with a **block size of 4** and stratified according to surgeon/specialty. In essence, each surgeon will receive their own list of randomized cases to simplify the logistics of the trial. **The block randomization guarantees that at no point during the trial will there be more than a 3-case difference between the treatment and control arms for each individual surgeon**; thus, it is possible but unlikely that there will be a maximum 9 case difference at some

point (sizes will be equal at completion). The randomization scheme has been pre-generated by a statistician, and the resulting trial arm for each case will be placed in envelopes to be revealed at the time of patient enrollment. The treatment will not be blinded to the physician or the patient; it is not practical to keep knowledge of the procedure concealed.

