 - b. Correction of unresolved diplopia (7 to 11 days) in the sitting of soft tissue prolapse with a positive forced duction test.
 - c. Immediate correction of diplopia in the sitting inferior rectus muscle incarceration and a positive forced duction test.
 - d. Immediate correction in a symptomatic patient with orbital floor (trapdoor) fracture that has elicited the oculocardiac reflex.
 - 3- At least 18 years of age.
 - 4- Unilateral orbital floor fracture.
 - 5- No history of orbital trauma.
 - 6- Healthy contralateral orbit.

- 7- Underwent orbital reconstruction.
- 8- Admitted to GMH.
- 9- Returned for the 6-week follow-up.
- Subjects will be excluded from the study enrollment if they:
 - 1- Refuse study enrollment.
 - 2- Are younger than 18 years.
 - 3- Pregnant women.
 - 4- Prisoner
 - 5- Unable to obtain consent (cognitively impaired)
 - 6- Are admitted to hospitals other than Grady Memorial Hospital.

Preoperative Assessment

- All patients, regardless of the group into which they are randomized, will receive a full history and physical examination as part of their admission, including past ocular history.
- A detailed ocular examination will be performed by the same ophthalmology team ([name], ophthalmology attending, or [name], ophthalmology fellow). The ophthalmology team will be blinded to the treatment group.
- This examination will include an evaluation of the following: visual acuity, intraocular pressure, extraocular motility, confrontation visual fields, pupil examination, external examination including Hertel exophthalmometer to document the degree of exophthalmos, slit lamp/penlight exam, dilated fundus exam, and binocular diplopia. These components make up the standard ophthalmologic examination performed for all orbital floor fractures. These data will be abstracted from the medical record before analysis.
- Maxillofacial non-contrast CT scans.
- **The additional workup for group A (treatment group) will include:**

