VSP and patient-specific implants represent the imminent future of the standard of care in surgery. The associated cost is a major hindrance, which is remarkable in a high-volume trauma setting that serves an underserved population (GMH). The proposed study tests the application of these technologies in an underserved population and correlates its use with a reduction in the overall health care cost.

This project will add significant value to the literature in this area. It will aid in the PI's development as a young craniomaxillofacial trauma researcher with an interest in an underserved population. This grant will also represent a vital step in the PI's career development toward an independent investigator based full-time at Grady Health System.

MENTORING PLAN

As the PI ([name]) is in her early research career and this will be her first prospective study, she will have guidance from the following mentors:

- 1- [name] [name], MDSc, FRACDS, FRACDS (OMS), FACS.
- 2- [name] [name], FACS.

[name] is the primary mentor. The PI will meet with him regularly for detailed research mentoring. [name] has wide-ranging research experience, particularly in facial trauma at GMH, where he conducted 2 EMCF-funded prospective studies in Grady (one of which was trauma-related). This experience will be valuable when mentoring for issues related to the conduct of facial trauma research at GMH. The PI will continue to meet with [name] at least monthly for 2 hours for focused mentoring and the discussion of all aspects of the ongoing study.

The PI will also meet with [name]. [name] will be the secondary mentor and is an eminent national and international figure in the field of oral and maxillofacial surgery. [name] is an established educator and is widely known in oral and maxillofacial surgery. The PI will meet with him monthly to discuss research progress and future directions. [name] will also review and collaborate on all manuscripts prepared using this dataset.

HUMAN SUBJECT PROTECTIONS

The following strategies will be used to protect the subjects:

1. All patients with orbital fracture will be offered the opportunity to participate in this study. If they decline, they will still receive the same care and treatment provided by the study.
2. All patients will have the protocol and study rationale explained to them. They will be asked to vocalize their understanding by explaining the same protocol and rationale back to the interviewer.

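### Patients listed for immediate correction can be randomised, but only Group A must wait for a printed, bent and sterilised plate, and no rule covers a patient whose surgery should not wait

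*Combined protocol and SAP*

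**What the plan says.** Under Inclusion & Exclusion Criteria, item 2 lists the indications for repair. Item 2b concerns diplopia still unresolved at 7 to 11 days. Item 2c is "Immediate correction of diplopia in the sitting inferior rectus muscle incarceration and a positive forced duction test". Item 2d is "Immediate correction in a symptomatic patient with orbital floor (trapdoor) fracture that has elicited the oculocardiac reflex". None of the six exclusions concerns urgency. Human Subject Protections, item 1, adds: "All patients with orbital fracture will be offered the opportunity to participate in this study".

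On allocation, Randomization & Statistical Analysis says that "the resulting trial arm for each case will be placed in envelopes to be revealed at the time of patient enrollment".

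The arms then differ in what must happen before theatre. Background describes the control plate as a "standard stock orbital plate, which is adapted intraoperatively to the fractured orbit". Preoperative Assessment sets out further work for Group A only: segmentation and mirroring of the CT, printing by two designated people, bending supervised by an attending, and dispatch to sterile processing.

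Background shows that the authors had timing in mind. It says "Reconstruction of the orbital fracture is time-sensitive to prevent unfavorable long-term sequelae", and that with an office printer "true-to-life anatomic models can be made on-site within hours".

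**The concern.** Randomisation presumes that either arm can be delivered to the patient who is enrolled. Here two entry criteria are worded as immediate, while one arm has a preparation step that starts only after allocation. The plan does not ask whether the patient can wait, sets no limit on the wait, and does not say what happens if a Group A patient must go to theatre before the plate is ready.

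What is at stake is mainly the care of that patient. Either surgery is delayed against the protocol's own indication, or the surgeon uses a plate that was not pre-bent. The second is a statistical matter as well. The change can run only from A to B, it would be decided by an unblinded surgeon after allocation, and the plan states no rule that patients are analysed in the arm to which they were randomised.

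**Working it through.** **Sequence in the text**

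| Step | Group A | Group B |
|---|---|---|
| Work-up, CT, consent | yes | yes |
| Envelope opened | at enrolment | at enrolment |
| Segmentation and printing | after allocation; model within hours | none |
| Bending on the model | after allocation; no time given | none before theatre |
| Sterile processing of the bent plate | after allocation; no time given | no such step described |
| Check that the patient can wait | none | not needed |

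The extra wait therefore falls on one arm, and its total length is not stated.

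**Reproducing the sample size.** Randomization Sample Size & Calculation gives a difference of 1 cm³, SD 1.17 cm³, alpha .05 (taken as two-sided), power 90% and 60 patients. The standardised difference is 1/1.17 = 0.855. The noncentral t calculation gives 29.76 per arm, rounded up to 30, so 60 in total. Power at 30 per arm is 90.2%. With a 25% shortfall (22.5 per arm) it is 80.0%. All of this agrees with the plan.

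**Effect of a one-way change to stock plates.** Let p be the share of Group A that receives an unbent plate, has the Group B mean, and is analysed in Group A. The protocol gives no value for p, so every value here is an assumption.

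- Expected difference = (1 − p) × 1 cm³.
- Fixed SD: 1.17 in both arms.
- Mixed-plate SD: Group A variance = 1.17² + p(1 − p) × 1², averaged with the Group B variance of 1.17².

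For p = 3/30 = 0.10 the difference is 0.90. The Group A variance is 1.3689 + 0.09 = 1.4589, the average variance is 1.4139, and the SD is 1.189.

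| Assumed changes in Group A | Difference (cm³) | Power, fixed SD | Power, mixed-plate SD |
|---|---|---|---|
| 0 of 30 | 1.00 | 90.2% | 90.2% |
| 3 of 30 | 0.90 | 83.4% | 82.2% |
| 4 of 30 | 0.87 | 80.5% | 78.9% |
| 6 of 30 | 0.80 | 74.0% | 71.6% |

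A simulation with exactly 3 changes (200,000 runs) gave 82.6%. Power reaches 80% at p of about 12% (mixed-plate SD) to 14% (fixed SD).

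**If such patients were dropped instead.** With 27 in Group A and 30 in Group B, power would be 88.6%. The removal would be from one arm only, which opens a selection bias that the power figure does not show.

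**Predictability of allocation**, which bears on the fix. A block of 4 has 6 possible orders, so 24 positions. In 8 of these, both places of one arm are already used and the allocation is certain: 8/24 = one third, for anyone who knows the block size and the earlier allocations.

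**The case against.** The strongest reply is that *immediate* is undefined and sits directly after an item about 7 to 11 days. It may mean only that no observation period is needed, in which case preparation taking hours does not breach it. This is a fair reading of 2c. It fits 2d less easily, because 2d rests on an elicited reflex and not on diplopia that might resolve.

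The authors also chose office printing because they found the 7–14 day production time of manufactured implants too long, and they present the new method as fast. Work-up, CT and consent are common to both arms and may absorb part of the wait. Enrolment is voluntary, and the offer of the trial to all patients does not override the eligibility list. The data table already records the indication, the use of a model, the printing time and the time from admission to surgery, so delays would be visible afterwards.

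All of this stands, and it limits the claim. A reader might infer that the trial randomises patients who cannot safely receive Group A. The documents do not support that: they give no safe waiting time and no total preparation time. Nor do they support a claim that a wait of hours alters orbital volume on the immediate postoperative CT.

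What the reply leaves open is the missing rule. Recording a delay is not a check before allocation, and the stated hours are attached to the model, with no time for bending or sterilisation.

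**Conclusion.** The concern holds as a gap between eligibility and deliverability. The criteria, followed exactly, can place a patient with an immediate indication in the arm that must wait for its plate, and the plan has no check or fallback for this. It is a possible safety conflict of unknown frequency and unknown duration.

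The statistical consequence is likely minor. Only patients who have 2c or 2d, cannot wait, and are then given an unbent plate contribute to it. An assumed 10% of Group A costs about 7 to 8 percentage points of power. The loss would be material if the share were nearer 20%, but nothing in the protocol suggests a value. These figures assume a true 1 cm³ effect, analysis as randomised, and Group B results in patients given an unbent plate. The case for a change rests on the individual patient, not on power, and the change is cheap enough to make without knowing the frequency.

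**What to change.** 1. State the expected time from CT to sterile pre-bent plate.
2. Add an eligibility condition. Before the envelope is opened, the treating surgeon records the indication (2a to 2d) and confirms that surgery can wait that long. The surgeon is the right recorder: the ophthalmology examination listed under Preoperative Assessment includes neither forced duction nor the oculocardiac reflex.
3. Treat patients who cannot wait outside the trial, and enter them in a screening log with the reason. Patients with 2c or 2d who can wait stay eligible.
4. If a randomised Group A patient must still go to theatre before the plate is ready, use a stock plate, record the plate implanted, and analyse the patient in Group A.

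**Cost.** This takes a short amendment, one recorded check and a log. The target stays at 60 randomised. If an assumed 5%, 10% or 20% of otherwise eligible patients could not wait, 60/(1 − share) gives 64, 67 or 75 to be screened. The results would not apply to patients who cannot wait.

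The check adds a small selection risk. Treatment is unblinded, blocks have size 4, and "each surgeon will receive their own list of randomized cases to simplify the logistics of the trial", so some allocations can be foreseen by the person making the judgement. Recording the criterion before the envelope is opened, and keeping the log, limit that risk.

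A lighter option is step 4 alone. It loses no patients, but it still randomises some who may be unable to receive Group A treatment.

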The success of the randomization will be evaluated at the start of the analysis by comparing patient characteristics. Differences between the treatment and control arms that do not reach statistical significance using appropriate tests (likely t-tests and chi-square tests) that are smaller than 20% for all characteristics will mean that the groups are ‘balanced’ in our criteria and will be evidence of randomization success. Assuming that standardization is successful, all outcomes will be compared using standard two-sample comparisons. For binary outcomes, such as complications and CT use, Chi-square tests or Fisher’s exact tests will be used depending on the prevalence of the outcome. Two-sample t-tests or Wilcoxon-Mann-Whitney tests (if data are non-parametric) will be used to compare mean orbital volume differences and operative times. Differences in length of stay and costs are likely to be analyzed with two sample t-tests on a log scale (thus, a comparison of geometric means will be made). Finally, logistic regression or other multivariable analyses may be performed to identify risk factors for developing complications or deviations from the normal recovery course.

Statistical Support

Support for statistical analyses will be provided by [name], MSPH, a trained biostatistician, working for the Department of Surgery at Emory University Hospital. All analyses will be conducted or supervised by [name]. [name] has 15 years of experience in data analysis and 7 years of experience working as the department statistician for surgery. He has over 40 peer-reviewed publications to his name and experience with outcomes and health services research as well as basic science research. In the past, he has assisted in the design and analysis of similar trials at Emory University. Regarding the cost-effective analysis, [name] is the primary mentor. He is an experienced researcher and participated in cost-effective research in GMH by comparing the cost effectiveness of 2 types of mandibular fracture treatment. ⁽²⁴⁾

Inclusion & Exclusion Criteria

- The following subjects will be included in the study:
 - 1- Agreed to be enrolled in the study.
 - 2- Indications for surgical repair of orbital floor and/ wall fractures are dependent on several factors:
 - a. Correction or prevention of cosmetic deformity (enophthalmos or inferior dystopia; disruption of greater than 50% of the orbital floor is likely to cause cosmetically apparent enophthalmos.

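### Return at six weeks is listed as an inclusion criterion, though it is known only after randomisation and after the primary CT; no analysis set says whether scanned non-returners count

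*Combined protocol and SAP*

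**What the plan says.** - **Inclusion & Exclusion Criteria.** The inclusion list opens with "The following subjects will be included in the study", and its item 9 is "Returned for the 6-week follow-up". Item 7 likewise requires that reconstruction has taken place.
- **Randomization & Statistical Analysis, allocation.** Assignments are "placed in envelopes to be revealed at the time of patient enrollment". On masking: "The treatment will not be blinded to the physician or the patient".
- **Study Settings and Patients; Postoperative Assessment, item 2.** The primary outcome is the volume of the injured orbit against the uninjured one, measured on the CT taken immediately after surgery.
- **Randomization Sample Size & Calculation.** The plan considers "in the event of attrition from loss-to-follow-up alone, our primary outcomes variable and the bulk of the secondary outcomes variables" and expects these to have been collected already. It concludes: "Attrition at these stages will have no effect on the above variables". Separately, it states that power would still be 80% "if 25% of our expected patient enrollment numbers are not met for any reason".
- **Randomization & Statistical Analysis, methods.** The comparison is described as "Assuming that standardization is successful, all outcomes will be compared using standard two-sample comparisons". No intention-to-treat, per-protocol or other analysis set is named, and there is no rule for patients who do not return.

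**The concern.** An eligibility criterion should be decidable before allocation. Item 9 is decided after allocation, after surgery and after the primary outcome has been measured. Read literally, a patient who was randomised, operated on and scanned but who misses week 6 is not an included subject, and a primary measurement already in hand is discarded. The sample size section treats that same patient as contributing to the primary outcome. The two sections therefore give different primary analysis sets.

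Three things are at stake:

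- **Discretion.** An analyst could follow either section and claim to comply with the protocol, and could choose after seeing results.
- **Selection after randomisation.** Patients and surgeons know the arm. If the decision to return depends on how well the repair went, and does so differently by arm, restricting the analysis to returners biases the comparison. This is possible; nothing in the protocol shows that it happens.
- **Precision.** Measured primary outcomes are thrown away.

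**Working it through.** **Order of events for one patient.** Enrolment and opening of the envelope; surgery; immediate post-operative CT (primary outcome); visits at weeks 1, 3 and 6. Item 9 is settled only at the last step.

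**Inputs from Randomization Sample Size & Calculation.** N = 60, split evenly; target difference 1 cm³; SD 1.17 cm³; alpha 0.05; power 90%; 80% power after a 25% shortfall. Sidedness is not stated. A two-sided test reproduces N (a one-sided test would need only 25 per arm).

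**Reproducing the plan's figures.** Two-sample t-test, noncentral t, with noncentrality = 1 / (1.17 × √(2/n)) and 2n − 2 degrees of freedom.

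- 90% power requires 29.76 per arm, so 30 per arm and N = 60. At n = 30 the noncentrality is 1 / 0.3021 = 3.31 and power is 90.2%.
- At N = 45 (n = 22.5 per arm) the noncentrality is 1 / 0.3488 = 2.87 and power is 80.0%.

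Both stated figures are correct.

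**Loss of precision if item 9 is applied.** The non-return rates are assumed; loss is equal in both arms and non-returners are not replaced. CI half-width = t(0.975, 2n − 2) × 1.17 × √(2/n).

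| Non-return | CTs discarded | n per arm | Power for 1 cm³ | 95% CI half-width (cm³) |
|---|---|---|---|---|
| 0% | 0 | 30 | 90.2% | 0.61 × 1 = 0.61 (t = 2.002 × 0.3021 = 0.605) |
| 5% | 3 | 28.5 | 88.7% | 0.62 |
| 10% | 6 | 27 | 86.9% | 0.64 |
| 25% | 15 | 22.5 | 80.0% | 0.70 |

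**Bias if item 9 is applied.** Let f be the fraction lost in an arm and g the returner mean minus the non-returner mean in that arm. Then bias = f_A × g_A − f_B × g_B. Type I error is the rejection probability of the same t-test when the true difference is 0 and the observed difference is centred on the bias. SD 1.17 is assumed among returners. Every f and g is an assumption.

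| Loss, each arm | Gap in arm A (cm³) | Gap in arm B (cm³) | Bias (cm³) | Type I error |
|---|---|---|---|---|
| 25% | 1 | 1 | 0.25 × 1 − 0.25 × 1 = 0 | 5.0% |
| 10% | 0.5 | 0 | 0.10 × 0.5 = 0.05 | 5.3% |
| 25% | 0.5 | 0 | 0.25 × 0.5 = 0.125 | 6.4% |
| 25% | 1 | 0 | 0.25 × 1 = 0.25 | 10.8% |

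The last row needs a gap in one arm as large as the whole target difference.

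**The case against.** The strongest reply is that item 9 was meant as willingness to return.

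- The sample size section is the only place that discusses loss to follow-up and the primary outcome together, and it expects the primary outcome to survive.
- Patient Compensation pays all enrolled patients, partly for completing week 6, which treats non-returners as still enrolled. The payment may also reduce non-return.
- The exclusion list does not mention non-return, and no analysis sentence applies item 9.
- The plan expects equal arm sizes at the end, which fits counting all randomised cases.
- Much of the inclusion list is loosely drafted in the past tense.

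All of this stands as evidence of intent, and the milder reading is plausible. It does not remove the conflict. The sample size section says when data are obtained; it does not define who is analysed, and item 9 says returned, not willing to return.

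The second reply is that the harm is hypothetical. That also stands. No non-return rate is given, the 80% power figure is already disclosed, and the non-zero bias rows put the gap in one arm only. If the other arm has half the gap, the same three rows give bias of 0.025, 0.0625 and 0.125 cm³ and type I error of 5.1%, 5.4% and 6.4%. The case for correction rests on the criterion being undecidable at enrolment and in conflict with another section, whichever scenario is believed.

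Third, requiring a post-operative CT is itself a condition met after allocation, and missing week-6 secondary outcomes need their own rule. Both points are fair and are taken up in the fix. Item 7 discards no CT and is a matter of wording only.

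**Conclusion.** The concern holds and should be corrected. Item 9 as written conditions inclusion on an event after randomisation and after the primary measurement, it contradicts the plan's own statement about attrition, and no defined analysis population resolves the contradiction.

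The effect on power is modest and, up to 25% loss, within what the plan already accepts. The more serious consequence is that the randomised comparison could be restricted to returners in an open-label trial. Over the one-arm scenarios examined, bias runs from 0.05 to 0.25 cm³ against a 1 cm³ target; it is zero if loss and the returner/non-returner gap are equal in both arms. These sizes rest on assumed loss rates and gaps, with SD 1.17 cm³ and a two-sided test. Neither the size nor the direction of any actual bias can be learned from the protocol.

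**What to change.** 1. Reword item 9 as a condition that can be judged at enrolment: willing to attend the 6-week visit. For consistency, reword item 7 as planned for reconstruction.
2. In Randomization & Statistical Analysis, define the primary analysis set as all randomised patients with an immediate post-operative CT, analysed in the assigned arm whether or not they return.
3. Report by arm the numbers not operated on, not scanned, and missing at week 6, so that any remaining selection is visible.
4. State how missing week-6 secondary outcomes will be handled, since that is where loss to follow-up has its real effect.

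The cost is protocol wording only, with no extra patients or procedures. The drawback is that some patients in the primary analysis will have no week-6 data. The change brings the eligibility list into line with what the sample size section already promises.
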